5. GENERAL METHODOLOGY AND CONVENTIONS

Methodology for summary and statistical analyses of the data collected in this study is described here. The SAP may modify what is outlined in the protocol where appropriate; however, any major modifications of the primary endpoint definitions or their analyses will also be reflected in a protocol amendment.

This is an open-label study. Participants, site personnel, and Pfizer staff are not blinded to the participants' assigned study intervention. The timing for statistical analysis is specified in [Section 7.3](#).

5.1. Hypotheses and Decision Rules

5.1.1. Immunogenicity Hypotheses

There is no statistical hypothesis testing planned for this study. All statistical analyses are descriptive and for estimation purposes.

5.1.2. Multiplicity Adjustment

No multiplicity adjustment is needed, as there is no statistical hypothesis.

5.2. General Methods

CI for all endpoints in the statistical analysis will be presented as 2-sided at the 95% level unless specified otherwise.

5.2.1. Analyses for Binary Endpoints

Descriptive statistics for categorical variables (eg, proportions) are the percentage (%), the numerator (n) and the denominator (N) used in the percentage calculation, and the 95% CIs, where applicable.

The exact 95% CI for binary endpoints for each group will be computed using the F distribution (Clopper-Pearson method).¹

5.2.2. Analyses for Continuous Endpoints

Unless otherwise stated, descriptive statistics for continuous variables are n, mean, median, standard deviation, minimum, and maximum.

5.2.3. Geometric Means

The geometric means will be calculated as the mean of the assay results after making the logarithm transformation and then exponentiating the mean to express results on the original scale. Two-sided 95% CIs will be obtained by taking log transforms of assay results, calculating the 95% CI with reference to the Student t distribution, and then exponentiating the confidence limits.

5.2.4. Geometric Mean Fold Rises

GMFRs are defined as ratios of the results after vaccination to the results before vaccination. GMFRs are limited to participants with nonmissing values at both time points.

GMFRs will be calculated as the mean of the difference of logarithmically transformed assay results (later time point minus earlier time point) and exponentiating the mean. The associated 2-sided 95% CIs will be obtained by constructing CIs using the Student t distribution for the mean difference on the logarithm scale and exponentiating the confidence limits.

5.2.5. Reverse Cumulative Distribution Curves

Empirical RCDCs will plot proportions of participants with values equal to or exceeding a specified assay value versus the indicated assay value, for all observed assay values. Data points will be joined by a step function with data points on the left side of the step.

5.3. Methods to Manage Missing Data

In general, completely missing reactogenicity data (ie, all 7 days of collection were missing) will not be imputed. For partially missing reactogenicity data (ie, 1-6 days of reactogenicity data are available), it is assumed that no reactions or events were experienced on the missing days.

A partial AE start date (missing day or missing both month and day) will be imputed by assigning the earliest possible start date using all available information, such as the stop date of the AE and the study vaccination date(s) from the same participant, following the Pfizer standard for handling an incomplete AE start date. A complete missing start date for an AE is not allowed in the data collection.

Missing serology results will not be imputed. Immunogenicity results that are below the LLOQ will be set to $0.5 \times \text{LLOQ}$ in the analysis; this may be adjusted once additional data on the assay characteristics become available.

No additional imputation will be applied to other missing data.

6. ANALYSES AND SUMMARIES

6.1. Primary Endpoints

6.1.1. Safety Primary Endpoints

The analyses specified in this section apply to Cohort 1 and Cohort 2 combined and Cohort 3.

6.1.1.1. Local Reactions

6.1.1.1.1. Main Analysis

- Estimand: The percentage of participants reporting local reactions (redness, swelling, and pain at the injection site) for up to 7 days after the study vaccination ([Section 2.2](#)).
- Analysis set: Safety population ([Section 4](#)).
- Analysis time point: Up to 7 days after the study vaccination.
- Analysis methodology: Descriptive statistics ([Section 5.2.1](#)).
- Intercurrent events and missing data: Missing data will be handled as described in [Section 5.3](#).

- Reporting results: Descriptive statistics for each and any local reaction after the study vaccination in each age subgroup (12-17 years [for Cohort 2 only], 18-55 years, >55 years) and overall will be presented by maximum severity and cumulatively across severity levels. Descriptive summary statistics will include counts and percentages of participants with the indicated endpoint and the associated 2-sided Clopper-Pearson 95% CIs.

6.1.1.1.2. Supplemental Analysis

To support the assessment of local reactions, the following endpoints (as defined in [Section 3.1.1.1](#)) will be summarized with the same analysis time point and analysis population as above and the appropriate analysis methodology and reporting results:

- Duration (days) of each local reaction after the study vaccination.
- Onset day of each local reaction after the study vaccination.

These continuous endpoints will be summarized by displaying n, mean, median, standard deviation, minimum, and maximum by age subgroup (12-17 years [for Cohort 2 only], 18-55 years, >55 years) and overall.

Figures:

Bar charts with the proportions of participants for each local reaction throughout 7 days after the study vaccination will be plotted by age subgroup (12-17 years [for Cohort 2 only], 18-55 years, >55 years) and overall. The bars will be divided into severity categories to highlight the proportions of participants by maximum severity.

6.1.1.2. Systemic Events

6.1.1.2.1. Main Analysis

- Estimand: The percentage of participants reporting systemic events (fever, fatigue, headache, chills, vomiting, diarrhea, new or worsened muscle pain, and new or worsened joint pain) for up to 7 days after the study vaccination ([Section 2.2](#)).
- Analysis set: Safety population ([Section 4](#)).
- Analysis time point: Up to 7 days after the study vaccination.
- Analysis methodology: Descriptive statistics ([Section 5.2.1](#)).
- Intercurrent events and missing data: Missing data will be handled as described in [Section 5.3](#).

- Reporting results: Descriptive statistics for each systemic event after the study vaccination in each age subgroup (12-17 years [for Cohort 2 only], 18-55 years, >55 years) and overall will be presented by maximum severity and cumulatively across severity levels. Descriptive summary statistics will include counts and percentages of participants with the indicated endpoint and the associated 2-sided Clopper-Pearson 95% CIs.

6.1.1.2.2. Supplemental Analysis

The following endpoints for the assessment of systemic events will be summarized similarly to the assessment of local reactions:

- Duration (days) of each systemic event after the study vaccination.
- Onset day of each systemic event after the study vaccination.

These continuous endpoints will be summarized by displaying n, mean, median, standard deviation, minimum, and maximum by age subgroup (12-17 years [for Cohort 2 only], 18-55 years, >55 years) and overall.

Figures:

Bar charts with the proportions of participants reporting each systemic event throughout 7 days will be plotted for each age subgroup (12-17 years [for Cohort 2 only], 18-55 years, >55 years) and overall. The bars will be divided into severity categories to highlight the proportions of participants by maximum severity.

6.1.1.3. Adverse Events

6.1.1.3.1. Main Analysis

- Estimand: The percentage of participants reporting AEs from the study vaccination through 1 month after the study vaccination ([Section 2.2](#)).
- Analysis set: Safety population ([Section 4](#)).
- Analysis time point: From the study vaccination through 1 month after the study vaccination.
- Analysis methodology: Descriptive statistics ([Section 5.2.1](#) and [Section 3.1.1.3](#)).
- Intercurrent events and missing data: Missing data will not be imputed, except for partial AE start dates ([Section 5.3](#)).
- Reporting results: Counts, percentages, and the associated 2-sided Clopper-Pearson 95% CIs of AEs within 1 month after the study vaccination will be provided for each age subgroup (12-17 years [for Cohort 2 only], 18-55 years, >55 years) and overall.

6.1.1.3.2. Supplemental Analysis

Related AEs, severe AEs, immediate events (within the first 30 minutes after the study vaccination), and AESIs (defined in Section 10.9.8.4.1 of the protocol) will also be summarized by age subgroup (12-17 years [for Cohort 2 only], 18-55 years, >55 years) and overall.

All AEs after informed consent and prior to the first vaccination will not be included in the analyses but will be in the listing.

6.1.1.4. Serious Adverse Events**6.1.1.4.1. Main Analysis**

- Estimand: The percentage of participants reporting SAEs from the study vaccination through 6 months after the study vaccination ([Section 2.2](#)).
- Analysis set: Safety population ([Section 4](#)).
- Analysis time point: From the study vaccination through 6 months after the study vaccination.
- Analysis methodology: Descriptive statistics ([Section 5.2.1](#)).
- Intercurrent events and missing data: Missing data will not be imputed, except for partial AE start dates ([Section 5.3](#)).
- Reporting results: Counts, percentages, and the associated Clopper-Pearson 95% CIs of SAEs from the study vaccination through 6 months after the study vaccination will be provided for each age subgroup (12-17 years [for Cohort 2 only], 18-55 years, >55 years) and overall.

6.1.2. Immunogenicity Primary Endpoints**6.1.2.1. Cohort 1 and Cohort 2 Combined****6.1.2.1.1. Main Analysis**

- Estimands:
 - GMTs of SARS-CoV-2 Omi JN.1–neutralizing titers and SARS-CoV-2 Omi XBB.1.5–neutralizing titers at 1 month after vaccination for each age subgroup (12-17 years [for Cohort 2 only], 18-55 years, >55 years) and overall.
 - GMFRs of SARS-CoV-2 Omi JN.1–neutralizing titers and SARS-CoV-2 Omi XBB.1.5–neutralizing titers from before the study vaccination to 1 month after the study vaccination for each age subgroup (12-17 years [for Cohort 2 only], 18-55 years, >55 years) and overall.

- Percentages of participants with seroresponse to SARS-CoV-2 Omi JN.1 and SARS-CoV-2 Omi XBB.1.5 at 1 month after vaccination for each age subgroup (12-17 years [for Cohort 2 only], 18-55 years, >55 years) and overall.
- Analysis sets: Evaluable immunogenicity population, all-available immunogenicity population (as applicable) ([Section 4](#)).
- Analysis time points: 1 Month after vaccination, from before the study vaccination to 1 month after the study vaccination (for GMFRs only).
- Analysis methodology: The GMTs and the associated 2-sided 95% CIs at 1 month after the study vaccination will be provided using the statistical methods described in [Section 5.2.3](#). The GMFRs and the associated 2-sided 95% CIs from before the study vaccination to 1 month after the study vaccination will be provided using the statistical methods described in [Section 5.2.4](#). The percentages of participants with seroresponse at 1 month after the study vaccination and the associated Clopper-Pearson 95% CIs will be provided ([Section 5.2.1](#)). Seroresponse is defined as achieving a ≥ 4 -fold rise from baseline (before the study vaccination). If the baseline measurement is below the LLOQ, the postvaccination measure of $\geq 4 \times \text{LLOQ}$ is considered seroresponse.
- Intercurrent events and missing data: Serology data deemed unevaluable because of noncompliance with the key protocol criteria will be excluded. Missing data will not be imputed.
- Reporting results: For the BNT162b2 (Omi JN.1) group in Substudy C Cohort 1 and Cohort 2 combined and the historical control of the BNT162b2 (Omi XBB.1.5) group from Substudy A, respectively, GMTs before and 1 month after the study vaccination, GMFRs from before the study vaccination to 1 month after vaccination, and percentages of participants with seroresponse to SARS-CoV-2 Omi JN.1 and SARS-CoV-2 Omi XBB.1.5 at 1 month after vaccination, along with the associated 2-sided 95% CIs, will be provided for each age subgroup and overall. The above analysis may be performed by baseline SARS-CoV-2 infection status if there is a sufficient number of participants without prior SARS-CoV-2 infection. Additionally, the above analysis may be performed by prior COVID-19 vaccine history at baseline (naïve or experienced) if there is a sufficient number of participants in both of these categories.

Figures:

Empirical RCDCs may be provided for SARS-CoV-2 Omi JN.1–neutralizing titers and SARS-CoV-2 Omi XBB.1.5–neutralizing titers before and 1 month after the study vaccination for each age subgroup. Bar charts of GMTs and the associated 2-sided 95% CIs will be provided for SARS-CoV-2 Omi JN.1–neutralizing titers and SARS-CoV-2 Omi XBB.1.5–neutralizing titers before and 1 month after the study vaccination for each age subgroup.

6.1.2.2. Cohort 3

6.1.2.2.1. Main Analysis

- Estimands:
 - GMTs of SARS-CoV-2 Omi KP.2–neutralizing titers and SARS-CoV-2 Omi JN.1–neutralizing titers at 1 month after vaccination for each age subgroup (18-55 years, >55 years) and overall.
 - GMFRs of SARS-CoV-2 Omi KP.2–neutralizing titers and SARS-CoV-2 Omi JN.1–neutralizing titers from before the study vaccination to 1 month after the study vaccination for each age subgroup (18-55 years, >55 years) and overall.
 - Percentages of participants with seroresponse to SARS-CoV-2 Omi KP.2 and SARS-CoV-2 Omi JN.1 at 1 month after vaccination for each age subgroup (18-55 years, >55 years) and overall.
- Analysis sets: Evaluable immunogenicity population, all-available immunogenicity population (as applicable) ([Section 4](#)).
- Analysis time points: 1 Month after vaccination, from before the study vaccination to 1 month after the study vaccination (for GMFRs only).
- Analysis methodology: The GMTs and the associated 2-sided 95% CIs at 1 month after the study vaccination will be provided using the statistical methods described in [Section 5.2.3](#). The GMFRs and the associated 2-sided 95% CIs from before the study vaccination to 1 month after the study vaccination will be provided using the statistical methods described in [Section 5.2.4](#). The percentages of participants with seroresponse at 1 month after the study vaccination and the associated Clopper-Pearson 95% CIs will be provided ([Section 5.2.1](#)). Seroresponse is defined as achieving a ≥ 4 -fold rise from baseline (before the study vaccination). If the baseline measurement is below the LLOQ, the postvaccination measure of $\geq 4 \times \text{LLOQ}$ is considered seroresponse.
- Intercurrent events and missing data: Serology data deemed unevaluable because of noncompliance with the key protocol criteria will be excluded. Missing data will not be imputed.
- Reporting results: For the BNT162b2 (Omi KP.2) group in Substudy C Cohort 3 and the historical control of the BNT162b2 (Omi JN.1) group from Substudy C Cohort 1 and Cohort 2 combined, respectively, GMTs before and 1 month after the study vaccination, GMFRs from before the study vaccination to 1 month after vaccination, and percentages of participants with seroresponse to SARS-CoV-2 Omi KP.2 and SARS-CoV-2 Omi JN.1 at 1 month after vaccination, along with the associated 2-sided 95% CIs, will be provided for each age subgroup and overall. The above analysis may be performed by baseline SARS-CoV-2 infection status if there is a sufficient number of participants without prior SARS-CoV-2 infection. Additionally, the above analysis may be performed by prior

COVID-19 vaccine history at baseline (naive or experienced) if there is a sufficient number of participants in both of these categories.

Figures:

Empirical RCDCs may be provided for SARS-CoV-2 Omi KP.2–neutralizing titers and SARS-CoV-2 Omi JN.1–neutralizing titers before and 1 month after the study vaccination for each age subgroup. Bar charts of GMTs and the associated 2-sided 95% CIs will be provided for SARS-CoV-2 KP.2–neutralizing titers and SARS-CoV-2 Omi JN.1–neutralizing titers before and 1 month after the study vaccination for each age subgroup.

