## Protocol Amendment Summary of Changes Table

### Amendment 2 (07 August 2024)

#### Overall Rationale for the Amendment:

This amendment adds Cohort 3 to Substudy C for the evaluation of BNT162b2 (Omi KP.2) in response to the US FDA/CBER's recommendation on 13 June 2024 for updated COVID-19 vaccines to target the Omicron KP.2 strain, if feasible. Participants 18 years of age and older will be enrolled into Cohort 3 for the evaluation of the safety, tolerability, and immunogenicity of BNT162b2 (Omi KP.2). Cohorts 1 and 2, evaluating BNT162b2 (Omi JN.1), are already enrolled and are ongoing; the second investigational vaccine planned to be evaluated in Cohort 1 has been removed, since the evaluation will be performed in Cohort 3 instead.

Description of Change	Brief Rationale	Section # and Name
Substantial Modifications		
Added more recent data for the prevalence of most common SARS-CoV-2 variants in the US.	Prevalence of variants has considerably changed since the writing of protocol amendment 1.	Section 1.1 Synopsis, Section 2.2 Background
Added statements that Omicron KP.2 is the vaccine strain recommended for the 2024-2025 season by the US FDA, if feasible.	To comply with the FDA's recommendation on 13 June 2024.	Section 2.1 Study Rationale, Section 10.9.2.1 Study Rationale
Added a brief summary of the preclinical data on the immunogenicity of KP.2- and JN.1-adapted vaccines presented at the FDA's VRBPAC meeting on 05 June 2024.	To provide a rationale for the clinical evaluation of vaccines targeting SARS-CoV-2 Omicron KP.2 and Omicron JN.1 variants.	Section 2.1 Study Rationale
Updated the clinical overview to add newly reported data.	To provide recent data on Substudy B.	Section 2.2.1 Clinical Overview

Description of Change	Brief Rationale	Section # and Name
Updated text to add Cohort 3 and its analyses to Substudy C.	To evaluate the investigational vaccine targeting the SARS-CoV-2 variant recommended (if feasible) by the US FDA for the 2024-2025 season.	Section 1 Protocol Summary, Section 10.9 Appendix 9: Substudy C [multiple subsections]

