Since the start of the pandemic, a succession of antigenically divergent SARS-CoV-2 lineages have emerged, causing surges in infection rates. Since 2022, the Omicron lineage and many sublineages have caused almost all SARS-CoV-2 infections. With their emergence, they also demonstrated significant escape from established host immunity. The emergence of the BA.2.86 derivative JN.1 lineage and its sublineages over the last year have resulted in the diminished effectiveness of the XBB.1.5 vaccine. Based on weighted estimates in the US, for the 2-week period ending 03 February 2024, JN.1 accounted for 88.9% of all sequenced cases, with XBB.1.5 accounting for an estimated 0.0%. Based on the weighted estimates in the US, for the 2-week period ending 22 June 2024, the variant proportions of all sequenced cases at 5% or higher were: KP.3 at 27.1%, KP.2.3 at 12.3%, KP.2 at 10.7%, JN.1 at 9.2%, LB.1 at 8.6%, and KP.1.1 at 6.3%.

Currently available COVID-19 vaccines continue to provide effective protection against SARS-CoV-2, including substantial protection against hospitalization and death, but reports have suggested potential waning of effectiveness against severe illness several months following vaccination. Considering the expectation that the virus will continue to accumulate mutations and may evolve to more antigenically distant strains in the future, as well as the availability of clinical and real-world evidence indicating that better-matched vaccines improve protection, an update to a COVID-19 vaccine composition that closely matches the most predominant circulating sublineage(s) is justified. This update will improve vaccine-induced immune responses to circulating SARS-CoV-2 sublineages in preparation for annual autumn/winter respiratory virus seasons.

Based on this rationale, Pfizer-BioNTech will evaluate the following vaccine candidate(s):

- BNT162b2 (Omi XBB.1.5) in Substudy A and Substudy B
- BNT162b2 (Omi JN.1) in Substudy C, Cohort 1 and Cohort 2
- BNT162b2 (Omi KP.2) in Substudy C, Cohort 3

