### 2.1. Study Rationale

This protocol allows for the rapid initiation of clinical studies to evaluate the safety, tolerability, and immunogenicity of BNT162b2-based vaccines adapted to emerging variants (under monitoring, of interest, and/or of concern).

Since the start of the pandemic, a succession of antigenically divergent SARS-CoV-2 lineages have emerged, causing surges in infection rates. Since 2022, the Omicron lineage and its many sublineages have caused almost all SARS-CoV-2 infections. With their emergence, they also demonstrated significant escape from established host immunity. The emergence of the BA.2.86 derivative JN.1 lineage and sublineages over the last year have resulted in the diminished effectiveness of the XBB.1.5 vaccine. Based on weighted estimates in the US, for the 2-week period ending 03 February 2024, JN.1 accounted for 88.9% of all sequenced cases, with XBB.1.5 accounting for an estimated 0.0%. Based on the weighted estimates in the US for the 2-week period ending 22 June 2024,

the variant proportions of all sequenced cases at 5% or higher were: KP.3 at 27.1%, KP.2.3 at 12.3%, KP.2 at 10.7%, JN.1 at 9.2%, LB.1 at 8.6%, and KP.1.1 at 6.3%.

Currently available COVID-19 vaccines continue to provide effective protection against SARS-CoV-2, including substantial protection against hospitalization and death, but reports have suggested potential waning of effectiveness against severe illness several months following vaccination. Considering the expectation that the virus will continue to accumulate mutations and may evolve to more antigenically distant strains in the future, as well as the availability of clinical and real-world evidence indicating that better-matched vaccines improve protection, an update to a COVID-19 vaccine composition that closely matches the most predominant circulating sublineage(s) is justified. This update will improve vaccine -induced immune responses to circulating SARS-CoV-2 sublineages in preparation for annual autumn/winter respiratory virus seasons.

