#### **9.3.1.2.2. Geometric Mean Ratios**

##### **Model-Based GMR:**

As the primary approach, the GMR and associated 95% CI will be calculated by exponentiating the difference in LS means and the corresponding CIs based on analysis of logarithmically transformed assay results using a linear regression model that includes terms for baseline neutralizing titer, age, and comparison group.

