#### 10.9.4.3. Rationale for Comparator

For both Cohorts 1 and 2, Substudy A participants will be used as a historical comparator for immunogenicity for the matched time points. All Substudy A participants received BNT162b2 (Omi XBB.1.5) 30 µg as fourth or higher dose. This is the vaccine authorized for the 2023-2024 season and administered to individuals in the US since 11 September 2023. For Cohort 3, both JN.1 and KP.2 have been recommended as variant-adapted vaccines for the 2024-2025 season, therefore, Substudy C Cohorts 1 and 2, combined, will be used as a historical comparator for immunogenicity evaluation of BNT162b2 (Omi KP.2). All Cohort 1 and Cohort 2 participants will have received BNT162b2 (Omi JN.1) 30 µg.

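### Cohort 3 (KP.2) is set beside an earlier-enrolled, non-randomised JN.1 control using unadjusted summaries only; the baseline-adjusted contrast already defined in the protocol should be added

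*SAP*

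**What the plan says.** Protocol 10.9.4.3 states that "Substudy C Cohorts 1 and 2, combined, will be used as a historical comparator for immunogenicity evaluation of BNT162b2 (Omi KP.2"). The Amendment 2 rationale, dated 07 August 2024, says that "Cohorts 1 and 2, evaluating BNT162b2 (Omi JN.1), are already enrolled and are ongoing"; the same amendment adds Cohort 3.

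Substudy C SAP 6.1.2.2.1 gives, for the KP.2 group and for "the historical control of the BNT162b2 (Omi JN.1) group from Substudy C Cohort 1 and Cohort 2 combined, respectively", GMTs before and 1 month after vaccination, GMFRs, and seroresponse rates against KP.2 and JN.1, by age subgroup and overall. The methods in SAP 5.2.1 to 5.2.4 are per-group log means with t-based intervals and Clopper-Pearson intervals. Breakdowns by baseline infection status and by vaccine history are optional and depend on numbers. SAP 5.1.1 says: "There is no statistical hypothesis testing planned for this study. All statistical analyses are descriptive and for estimation purposes".

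Protocol 9.3.1.2.2 names as its primary GMR approach an analysis of log titers "using a linear regression model that includes terms for baseline neutralizing titer, age, and comparison group". Protocol 9.3.1.1 names the Miettinen-Nurminen method stratified by baseline titer and age for seroresponse differences. Protocol 10.9.9.3.1 refers Substudy C to 9.3.1, and the SAP for Substudies A and B uses both methods for Substudy B's own non-randomised comparison. The Substudy C SAP contains neither.

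**The concern.** The two groups were enrolled one after the other and may differ in recent infection, time since last dose and the share who are vaccine naïve. Substudy C admits naïve and experienced participants and does not require a known prior infection. Each of these factors acts on the Day 1 titer, and the Day 1 titer acts on all three primary immunogenicity summaries.

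Readers will look for the contrast between KP.2 and JN.1. The Cohort 3 objective names both vaccines, and protocol 2.1 mentions a preclinical trend toward higher KP.2 responses whose clinical size is undefined. With crude summaries alone, a difference caused by who was enrolled and when cannot be told from a difference between vaccines. The measures may also disagree with each other for the same reason.

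**Working it through.** **Inputs from the documents.** SD of log titer at 1 month 1.35, and a 20% nonevaluable rate (protocol 10.8.9.5, Substudy B). Cohort 3 about 100 and the JN.1 control about 200 (10.9.4.1). Substudy A fold rise against XBB.1.5 7.0 (95% CI 4.3, 11.4) with 67.6% seroresponse (2.2.1). Seroresponse is a rise of at least 4-fold.

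**Plan's own figure.** Substudy C states no power. Table 11 (Substudy B), which rests on the same SD, reproduces: 240 per group, SD 1.35 and margin 0.67 give 90.0%, 66.6% and 30.0% (noncentral t) at true GMR 1.0, 0.9 and 0.8, as printed.

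**Model with zero vaccine effect.** log(post) = a + b·log(baseline) + error. If the Cohort 3 baseline is F times the control's:

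- GMT ratio = F^b
- GMFR ratio = F^(b−1)
- seroresponse = Φ[(ln GMFR − ln 4)/SD of log fold rise]

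**Calibration.** The reported rates of 67.6%, 73.0% and 59.5% match 25/37, 27/37 and 22/37, so n = 37 is inferred. SD of log fold rise = [ln(11.4/4.3)/2]/2.028 × √37 = 1.46. Predicted seroresponse is Φ[(ln 7 − ln 4)/1.46] = 64.9%, against 67.6% reported. Slope b = (s² + 1.35² − 1.46²)/(2s²) for an assumed baseline SD s. With s from 0.8 to 1.6, b runs from 0.25 to 0.44; at s = 1.35, b = 0.41.

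**Results (F and b are assumptions).**

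| F | b | GMT ratio | GMFR ratio | Seroresponse change, points |
|---|---|---|---|---|
| 1.5 | 0.2 | 1.08 | 0.72 | −8.5 |
| 1.5 | 0.41 | 1.18 | 0.79 | −6.2 |
| 1.5 | 0.8 | 1.38 | 0.92 | −2.1 |
| 2 | 0.2 | 1.15 | 0.57 | −14.8 |
| 2 | 0.41 | 1.33 | 0.66 | −10.8 |
| 2 | 0.8 | 1.74 | 0.87 | −3.6 |

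At b = 0 only fold rise and seroresponse move, at b = 1 only GMT moves, and above 1 all three rise together. If the Cohort 3 baseline is lower, the signs reverse: F = 1/1.5 with b = 0.41 gives 1/1.18 = 0.85 for GMT and 1/0.79 = 1.27 for GMFR.

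**How large might F be?** If a fraction p of Cohort 3 had an extra infection raising baseline titer k-fold, F = k^p. Assuming p = 0.05 to 0.25 and k = 3 to 8, F runs from 3^0.05 = 1.06 to 8^0.25 = 1.68. With b = 0.5 the GMT ratio is then 1.03 to 1.30 and the GMFR ratio 0.97 to 0.77.

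**What adjustment does.** I simulated 3,000 trials of 80 versus 160 evaluable participants (100 × 0.8 and 200 × 0.8) with F = 2, b = 0.41 and no vaccine difference. Crude GMT and GMFR contrasts had opposite signs in 91% of runs. The regression on baseline and group gave a GMR of 1.00, and its interval excluded 1 in 4.7%. By construction, baseline titer carries the whole cohort difference in this simulation.

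**Precision.** The 95% CI factor for the GMR is exp[1.96 × 1.35 × √(1 − r²) × √(1/80 + 1/160)]: 1.44 unadjusted, 1.37 at baseline correlation r = 0.5, and 1.30 at r = 0.7.

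**The case against.** The strongest reply is that no between-group comparison is planned. The objective is to describe each response, there is no ratio, margin or decision rule to corrupt, and the sample size rests on no test. This stands: the issue bears on interpretation only. It does not make the point empty, since the SAP describes its analyses as estimation and labels the second group a control.

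Prevaccination GMTs are reported and charted, so an imbalance would be visible. This also stands, but seeing an imbalance does not say how much of the 1-month difference it explains. The infection-status split is optional and may not be run. At the 77.5% infection-induced seroprevalence quoted for late 2022, about 100 × 0.225 ≈ 22 Cohort 3 participants would lack prior infection. Nor does the split separate recent from older infection.

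A reader might infer that the control was vaccinated in a JN.1 period and Cohort 3 in a KP period, because "JN.1 accounted for 88.9% of all sequenced cases" in early February 2024 and the June figures are "KP.3 at 27.1%, KP.2.3 at 12.3%, KP.2 at 10.7%, JN.1 at 9.2%, LB.1 at 8.6%, and KP.1.1 at 6.3"%. The documents do not support that. Amendment 1, which added Substudy C, is dated 11 March 2024, so no control participant was enrolled in the February window. The control could have enrolled at any time from then to 07 August 2024. Protocol 2.1 puts KP.2 at 14.8% by 25 May within that span, and 2.2 calls it dominant by late May. The gap between cohorts may be short.

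A reader might also infer that GMT must favour KP.2 while fold rise favours JN.1. That is one scenario. Protocol 2.2.1 reports GMTs, GMFRs and seroresponse all generally higher in baseline-positive participants of an earlier study. The same section's BA.2.86 result (higher baseline, similar 1-month GMT, GMFR 4.5 against 7.0) fits the fold-rise half, but it compares strains within the same people, not groups.

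Finally, baseline titer does not identify recent KP-lineage infection or capture all priming. This stands as a limit on any adjusted estimate.

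**Conclusion.** The point holds as a conditional one. Cohort 3's only comparator is non-randomised and earlier-enrolled. The planned summaries make no allowance for baseline differences, although the protocol has a method for doing so and uses it in Substudy B. Crude GMT, GMFR and seroresponse can therefore differ between cohorts with no vaccine difference.

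The size cannot be fixed from the documents. For a baseline shift of 1.5- to 2-fold and slopes of 0.2 to 0.8, the spurious GMT ratio is 1.08 to 1.74 and the GMFR ratio 0.57 to 0.92. For a shift near 1.06 the effect is negligible. The shift, its direction, the slope and the baseline SD are all assumptions. The SD of 1.35 and the fold-rise SD come from other strains and populations.

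No decision rule is affected. This is a worthwhile, inexpensive improvement to a descriptive analysis, not a defect that invalidates it.

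**What to change.** In Substudy C SAP 6.1.2.2.1, for each strain (KP.2 and JN.1) at 1 month, in participants aged 18 or older:

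- Add a descriptive model-based GMR (KP.2 group over JN.1 group) with 95% CI, using the protocol 9.3.1.2.2 regression on strain-specific baseline titer, age and group.
- Add the seroresponse difference with 95% CI by Miettinen-Nurminen, stratified by baseline titer and age as in 9.3.1.1.
- Keep the planned per-group summaries, and base any statement comparing KP.2 with JN.1 on the adjusted estimates.
- Tabulate month of vaccination by group.
- Label the contrast as non-randomised, with residual confounding possible from priming that baseline titer does not capture.

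The age limit matters because the control may hold up to 20 participants aged 12 to 17 and Cohort 3 holds none. Dropping all 20 leaves (200 − 20) × 0.8 = 144 evaluable controls and moves the unadjusted CI factor only from 1.44 to 1.45.

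No hypothesis test is needed. Day 1 titers and ages are already collected, so the cost is SAP wording and one or two tables. Protocol section 9 lets the SAP modify the outlined analyses, and since the primary endpoints and their planned summaries stay as they are, the change can be made in the SAP.
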